Sample size calculations were performed using the formula adapted by Lindsey to take advantage of the power gained from obtaining repeated measurements across time and eyes (Lindsey, 2001). Data from the Berkeley Infant Biometry Study (BIBS) were used to obtain an estimate of the within-subject/within-visit repeatability of refractive error and the correlation of these measurements across time. The standard deviation for change in refractive error from 3 to 9 months of age from infants with hyperopia $>+5.00\text{D}$ enrolled in BIBS was 1.17D. Data from Atkinson et al. suggests a standard deviation of 1.50D and Ingram et al. give a standard deviation for change is assumed to be 1.36D (Atkinson et al., 2000; Ingram et al., 2000). To provide the most conservative estimate of sample size, the standard deviation of change is assumed to be 1.50D. If a new, difficult, expensive treatment strategy is to be adopted, the benefit must be substantial. The ordinary decrease in hyperopia in uncorrected, highly hyperopic infants might be 1.2D to 1.34D (Atkinson et al., 2000; Ingram et al., 2000). We would expect that there would be little enthusiasm for this new approach if the decrease in hyperopia in treated infants was not on the order of 3.00D (an improvement compared to controls of 1.75D). Using these parameters, a sample size of 13 in each randomized group will be needed ($\alpha=0.05$, $\beta=0.1$, two-sided test). If we estimate that 10% of the infants may not complete the follow up, 30 infants need to be enrolled with 15 randomly assigned to each of the two randomized groups. The rather large difference relative to its standard deviation to be detected ($1.75/1.50 = 1.17$) along with the increase in power obtained by taking repeated refractive error measurements help to keep the sample size low. However, given the prevalence of high hyperopia (more than $+5.00\text{D}$) in the population of 3 months old infants, a sample size of 30 eligible infants (for randomization, not including the case series) is not trivial. Up to 10 eligible infants will be enrolled in the case series portion of the study. One of the major efforts in this project will be screening the 900 infants needed to find those that are eligible.

C. Measurement/Instrumentation

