Infants with refractive errors from $+5.00\text{D}$ up to $+7.00\text{D}$ who are randomized to standard therapy will receive no correction. Follow-up will occur on the same schedule as infants randomized to treatment: 1.5 months after the baseline examination and then every 3 months until completion at 18 months of age (6 follow-up visits after the baseline exam). Regular clinical care, if any is needed, will begin at the conclusion of follow up at 18 months. Infants in either the treatment or control group who have not achieved a refractive error of $<+3.50\text{D}$ in each eye by 18 months of age will be referred outside the study for an independent evaluation. This level of hyperopia is selected for referral at 18 months because of its association with an elevated level of risk for strabismus (Atkinson, Braddick, Robier, et al., 1996)

- iv. **Case Series Group.** Infants with a refractive error of $\geq+7.00\text{D}$ will receive treatment (same protocol as infants randomized to the treatment group of this study). The follow-up of the infants in this case series group is the same for those who are randomized to treatment.
- c. **Measurements.** The subject will be examined while seated in the parent's lap for all tests.
 - i. **Visual Acuity.** Preferential looking visual acuity with **Teller acuity cards** will be used to determine visual acuity without refractive correction. The Teller acuity cards will be presented at 55cm. The subject is observed through a center peephole of the acuity cards for preferential looking. Successively smaller patterns are presented until the subject either no longer displays preferential looking, or loses interest. Testing will be first be attempted monocularly but if the subject is resistant to occlusion, testing will be done binocularly. Final results are recorded in the subject's chart as the cycles/degree of the last card at which a response is noted in each eye.
 - ii. **Pupil testing.** Pupillary function is tested with a penlight for size, equality, shape, response to direct light, and consensual response.

- iii. **Version testing.** Versions are tested, with the examiner looking for any restrictions of yoked eye movements as the baby looks in different fields of gaze.

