f. **Development of Strabismus.** The subject population of this study is at risk for developing strabismus (Anker et al., 2004; Cotter, 2007; Pascual et al., 2014). This will be discussed with the parents of potential subjects during screenings and during the consent process prior to the baseline examination. If a subject develops a strabismus, the subject will be discontinued from treatment in the study. The subject cannot remain in either arm of the study because of the different standard of care in prescribing philosophy that occurs with the development of strabismus (typically providing a full refractive correction for hyperopia). The subject will remain in the study and will continue to be followed for observation of all study measurements and outcomes. The subject's parents will have the option of their child remaining under the care of [name] in the Ohio State University College of Optometry Pediatric clinic, or any other doctor within the Ohio State University College of Optometry, or seek or be referred to another provider for a second opinion or for patient care. Any visits or treatment of strabismus or any clinical sequelae of the strabismus would be at the discretion of the licensed eye care provider and separate from the study. Follow up visits related to the study will follow the same schedule and contain the same measurements listed in the protocol.

E. **Internal Validity.** There are no threats to internal validity. All procedures performed in the examination are standard procedures that have been performed frequently in other studies. Threats to external validity might be present in selection bias. The sample of patients to be recruited will be identified at Riverside Pediatrics Associates by screenings of age appropriate infants. The screenings will be performed by [name], [name], or a nurse that has been adequately trained. The age, gender, and ethnicity of these patients might not be a true representation of the general population of full term, healthy infants.

F. **Data Analysis.** All data analysis will be performed using SPSS (Version 24). Statistical significance will be assessed using two-sided tests with an alpha level of 0.05. Data from both eyes will be included in all analyses and techniques to control for intra-subject correlations will be used.

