The basic analysis will be a two-sample t-test comparison of the change in refractive error between the two groups at 9 months and again at 18 months of age. Analysis of Covariance (ANCOVA) will be used to compare the change in refractive error between the two treatment groups adjusting for any possible confounding variables. Refractive error at 3 months along with any other identified confounders will be included as covariates in the analysis. Randomization of infants into the two treatment groups should protect against confounding, however, testing will be performed and adjustments made for imbalances in confounders between groups.

The relationship of accommodative effort and accommodative lag with change in refractive error between 3 and 9, or 3 and 18 months will be analyzed by repeated measures analysis of variance. We will fit a linear functions describing the relationship between change in refractive error and accommodation as the repeated factor, either effort or lag. A significant effect for type of accommodation will indicate that the greater slope is the better explanation of the driving force for change in refractive error.

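### The 13 per group for 90% power takes credit for repeated visits that the planned treatment tests, on their natural reading, do not use

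*Combined protocol and SAP*

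**What the plan says.** The sample size paragraph (just before section C, Measurement/Instrumentation) uses a published formula in order to "take advantage of the power gained from obtaining repeated measurements across time and eyes". From an SD of change of 1.50D, a difference of 1.75D, two-sided alpha 0.05 and beta 0.1, it concludes that "a sample size of 13 in each randomized group will be needed". Allowing for 10% loss, it enrols 15 per group. It adds that "the increase in power obtained by taking repeated refractive error measurements help to keep the sample size low". Earlier infant data are said to have supplied the "repeatability of refractive error and the correlation of these measurements across time", but the paragraph gives no correlation across visits or between eyes, and no number of repeats.

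The schedule has "6 follow-up visits after the baseline exam" (section D.b.iii, Control group).

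Section F, Data Analysis, describes the basic treatment comparison as a "two-sample t-test comparison of the change in refractive error between the two groups at 9 months and again at 18 months of age". It then says that "Analysis of Covariance (ANCOVA) will be used to compare the change in refractive error between the two treatment groups", with 3-month refraction among the covariates. It also states: "Data from both eyes will be included in all analyses and techniques to control for intra-subject correlations will be used". The only repeated-measures analysis in that section relates accommodation to change in refraction, with accommodation as the repeated factor. It does not compare the randomized groups.

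**The concern.** The sizing takes two credits, one for visits and one for eyes. The analysis carries over only the one for eyes. A change score at 9 or at 18 months uses the baseline and one follow-up visit, and the other five follow-up visits add nothing to that test. The plan attributes part of its small sample to repeated measurement, does not say how much, and does not say which test has the 90% power.

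With 26 expected completers, a null result will be read against the claimed 90%. If the relevant power is nearer 81% to 85%, the chance of missing a true 1.75D benefit is 15% to 19% rather than 10%. The difference detectable with 90% power also moves above the 1.75D that the plan treats as the worthwhile benefit.

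**Working it through.** **Inputs, from the sample size paragraph.** Two-sided alpha 0.05; power 0.90; difference 1.75D; SD of change 1.50D; equal allocation; 13 per group; 10% loss. Not given: the correlation across visits, the correlation between eyes, the number of repeats, and whether 1.50D is per eye or per infant.

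**1. Try to reproduce 13 without any repeated-measures gain.**

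n = 2 × (1.960 + 1.282)² × (1.50/1.75)² = 15.44, so 16 per group (normal).

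Exact power (noncentral t) is 0.891 at 16 and 0.910 at 17, so 17 per group.

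The inputs alone do not return 13. Reaching it needs a variance factor of about 0.84 (normal: 13/15.44) or 0.77 (exact t). The plan does not report the factor it used. The allowance for loss does reproduce: 13/0.9 = 14.4, so 15.

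**2. Power at 13 per group, one visit, no gain.**

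Standardized signal = 1.75 / (1.50 × √(2/13)) = 2.974.

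- Normal: Φ(2.974 − 1.960) = 0.845.
- Exact t, 24 df: 0.814.
- Difference detectable with 90% power: 3.242 × 1.50 × √(2/13) = 1.91D (normal), or 1.99D (exact t).

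**3. Credit for eyes only.** Assume that 1.50D is a single-eye SD and that effect and SD are the same in both eyes. Averaging the eyes gives SD = 1.50 × √((1 + ρ)/2), where ρ is the inter-eye correlation of change. Power at 13 per group:

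| Assumed ρ | SD (D) | Exact t | Normal |
|---|---|---|---|
| 0.9 | 1.462 | 0.833 | 0.862 |
| 0.8 | 1.423 | 0.853 | 0.880 |
| 0.7 | 1.383 | 0.872 | 0.897 |
| 0.6 | 1.342 | 0.891 | 0.914 |
| 0.5 | 1.299 | 0.909 | 0.930 |

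90% is reached at ρ of about 0.55 or lower (exact t) or 0.68 or lower (normal). If 1.50D is already a per-infant value, there is no gain from eyes and step 2 applies.

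**4. Add the planned adjustment for 3-month refraction.** Multiply the SD by √(1 − r²), where r is the assumed correlation of baseline with change, and use 23 df. Exact-t power at inter-eye correlations 1 / 0.9 / 0.8 / 0.7:

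- r = 0.2: 0.828 / 0.847 / 0.865 / 0.883.
- r = 0.4: 0.874 / 0.890 / 0.906 / 0.921.

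**5. Other margins in the plan (exact t, no gain).** With all 15 per group completing, power is 0.869. At 13 per group it is 0.882 with the cited SD of 1.36D and 0.955 with the cited 1.17D.

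**6. What a credit for time could do if a test used it.** As an illustration, assume six follow-up visits, a common across-visit correlation v, and 1.75D at every visit. The variance factor is then (1 + 5v)/6 × (1 + ρ)/2. With ρ = 0.9, exact-t power at 13 is 0.864 / 0.894 / 0.922 at v = 0.9 / 0.8 / 0.7, so 90% needs v of about 0.78 or lower. This is an assumed form. The documents do not give the cited formula.

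**The case against.** The strongest reply is that 81% describes an analysis nobody plans. It ignores the second eye, which the plan puts in every analysis, and the adjustment for 3-month refraction. With both, some of the assumed combinations in step 4 exceed 0.90. The plan also took the largest of its three SDs and enrols 15 to retain 13. This stands in full: 81% is a lower bound for the stated inputs, not the expected power.

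A second reply is that the credit for time may not be wholly lost. The ANCOVA sentence names no visit, the techniques for intra-subject correlation are not specified, and the correlation across time might include that between baseline and follow-up, which a baseline-adjusted analysis does use. This lowers certainty. But the outcome is described as change, no model over visits is described for the treatment comparison, and one change score per test remains the natural reading.

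The gain from eyes is itself insecure. Infants may qualify on one eye, with anisometropia up to 1.50D allowed, so the fellow eye can lie below +5.00D and need not show the same effect.

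A reader might go further and infer that 13 is an arithmetic error, perhaps from a one-sided formula, since 2 × (1.645 + 1.282)² × (1.50/1.75)² = 12.6 rounds up to 13. The documents do not support that. They say two-sided, and a low enough inter-eye correlation alone would also give 13.

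**Conclusion.** The mismatch holds. The 90% rests partly on repeated visits, while the planned treatment tests, on their natural reading, each use one follow-up visit. The reported inputs therefore do not support 90% for those tests. The number 13 cannot be verified, which is different from its being wrong.

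At 13 per group, 1.75D and 1.50D, the floor is 81% (exact t) or 84% (normal). Where the true figure lies above that depends on whether 1.50D is per eye or per infant, on the inter-eye correlation, and on how strongly 3-month refraction predicts change. The plan gives none of these. The shortfall is modest and may vanish, so a reader should not conclude that the trial is underpowered. The cited SD of 1.17D is for change from 3 to 9 months, so it does not settle the 18-month test. Part of the text before the sample size paragraph was not available for this check, so correlations stated there cannot be excluded, although the paragraph appears self-contained.

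The point should be fixed: the plan relies on this figure and the correction is cheap.

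**What to change.** Name the comparison to which the power statement applies: change at one stated visit, both eyes, adjusted for 3-month refraction. Restate its power at 13 per group without the across-time gain, or give the difference detectable with 90% power (about 2.0D with no gain). State the inter-eye correlation used, say whether 1.50D is per eye or per infant, and show the no-gain 81% as the lower bound.

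Optionally, if the sponsor wants to keep the across-time credit, name as the treatment test a longitudinal model over the scheduled visits and both eyes with a visit-averaged contrast, and say that 1.75D refers to that contrast. This is a trade-off. If the effect builds up with age, the visit-averaged difference will be smaller than the one at 18 months. A contrast at 18 months alone would gain little from the other visits when data are complete, so the single-visit power would still apply.

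The cost is rewording the sample size and analysis paragraphs, with no extra infants, visits or measurements. The stated power may become slightly less favourable.

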The proposed protocol for this study differs from other early intervention studies. The current proposal will provide a greater amount of under-correction and will occur at a younger age. Results from a longitudinal study performed by the primary investigator of this study suggest that 1.00D of under-correction in a three-month old infant would result in a very small change between 3 and 9 months of age (Figure 1) (Mutti et al., 2005). Previous studies have used only 1.00 to 2.00D of under-correction in early intervention (Atkinson et al., 2000; Ingram et al., 2000). Based on the information provided in Figure 1, the range of effective emmetropization occurs between +1.00D and +4.00D of hyperopia. More aggressive under-correction (greater than 1.00D to 2.00D) would be needed in higher hyperopes to ensure that they reach the range of effective emmetropization between +1.00D and +4.00D. The effective range of emmetropization is addressed in more detail in Figure 2. If the emmetropization endpoint is defined as reaching a refractive error of $\leq +2.00$ D by 18 months of age, then 80% or more of early refractive errors of +4.00D or less at 3 months of age will resolve by 18 months of age using no intervention. For early refractive error between +5.00D to +7.00D, which is what is proposed in this study, the percentage that reach the emmetropization endpoint of $\leq +2.00$ D drops to between 50% and as low as 20%. The range of refractive errors outside of +5.00D and +7.00D appears to be outside of the effective range of emmetropization.

Previous studies initiated early correction treatment in the latter half of the first year of life (Atkinson et al., 2000; Ingram et al., 2000). The majority of the emmetropization process occurs before 9 months of age (Mutti et al., 2005). As children get older, hyperopia becomes less effective in promoting refractive changes. Hyperopic infants between 3 and 9 months of age show a decrease of hyperopia by an average of 0.81D while infants between 9 and 18 months show a decrease of only 0.23D (Mutti et al., 2009). Perhaps previous studies did not find a treatment effect because they initiated treatment too

[figure not shown]

Figure 1. The change in hyperopia between 3 and 9 months as a function of hyperopia at 3 months.

[figure not shown]

Figure 2. The probability of emmetropization at 18 months ($\leq +2.00$ D) as a function of refractive error at 3 months.

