- Normal pregnancy and delivery (including Cesarean section delivery but excluding serious complications or conditions such as eclampsia or rubella)
- Hyperopia of $\geq +5.00\text{D}$ in the spherical component of refractive error (most hyperopic meridian) in one or both eyes measured with cycloplegic retinoscopy using 1% cyclopentolate
 - Infants with a refractive error of $\geq +5.00\text{D}$ to $\leq +7.00\text{D}$ will be randomized to treatment or standard therapy (which is observation only)
 - Infants with a refractive error of $> +7.00\text{D}$ will receive treatment
- No astigmatism greater than 2.00D in either eye
- No anisometropia greater than 1.50D (spherical equivalent)
- No strabismus or previous history of difficulty with pupillary dilation
- No history of cardiac, liver, asthma, or other respiratory disease
- No history of ocular disease, retinal detachment, severe macular dragging, intraocular surgery, optic nerve hypoplasia, malformations of the eye, cortical visual impairment or active ocular inflammation
- No history of hydrocephalus, Down syndrome, or cerebral palsy, developmental delay, or seizure disorders.

If a subject presents with conditions such as pathology, or refractive error that is significant and suggests the presence of a pathological condition, an appropriate referral will be made.

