a. **Cycloplegic refractive error.** Refractive error will be measured using cycloplegic autorefraction and retinoscopy (1% tropicamide at the screening visit and 1% cyclopentolate at all follow up visits). Refractive error will also be measured with the following FDA-approved commercially available instrument:

i. **Welch Allyn Sure Sight Autorefractor**

b. **Accommodative accuracy.** Accommodation will be assessed with the following FDA-approved commercially available instrument:

i. **PowerRefractor**

D. Detailed study procedures

a. **Screening.** Topical tropicamide (1%) will be administered to an infant at their 2 month well-baby visit. Thirty minutes after instillation of tropicamide, the infant is placed the appropriate distance from the autorefractor and from the screener (35cm from the Welch Allyn SureSight, 67 cm for retinoscopy) for measurement of central cycloplegic refractive error. If the subject measures $\geq +5.00\text{D}$ sphere in one or both eyes via retinoscopy, the subject's parent will be given information regarding the study. If the parent(s) decides to participate, [name] (co-investigator) will schedule the patient and infant for the treatment phase of the study.

b. Treatment

i. **Randomization.** Subjects will be randomized to treatment or placebo (control) if their refractive error is $\geq +5.00\text{D}$ to $\leq +7.00\text{D}$ via retinoscopy. A random number generator will be run in SAS using the RANUNI function prior to the start of the study. Random numbers will be generated for 30 subjects (15 for each arm of the study), in a manner in which half of the numbers are even and half of the numbers are odd. In the program, it will be specified that there should be 15 subjects in each arm of the study giving a total of 30 subjects. The program will then scramble numbers in random to provide 15 subjects in each arm. In order from the sequence of random numbers, even numbers will represent subjects assigned to treatment and odd numbers will represent subjects assigned to the control group (standard therapy – observation).

Subjects with a refractive error of $+7.00\text{D}$ or higher will receive treatment as a Case Series.

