Compliance of glasses wear will be encouraged with parents. A calendar will be given to the parents at each visit to help keep track of the subject's compliance with glasses wear and prescribed vision therapy. Compliance will be monitored but infants will not be discontinued from the study for non-compliance with glasses wear.

- iii. **Control group – Standard Therapy.** Infants typically do not receive comprehensive eye examinations. Therefore infant hyperopia is most often neither detected nor corrected in the US at this time. Uncorrected infant hyperopia has no symptoms. Infant eye examinations are typically done only when a child presents with strabismus or pathology. As an example,

none of highly hyperopic ($>+4.00\text{D}$) three-month-olds from the BIBS study referred for clinical assessment received at correction from community eyecare providers. Therefore the current standard for treating hyperopia against which any new treatment must be judged is observation without correction. The alternative would be to provide full or 1.00D under-correction. It has already been shown that infants may not emmetropize with these corrections (Atkinson et al., 2000). Any inhibition of emmetropization may be accentuated if infants are corrected in this way at three months rather than later. Infants with no correction may occasionally emmetropize (Ingram et al., 2000). This suggests that the most ethical and informative form of standard therapy for infant hyperopia would be to provide no correction for the infants within the range of eligibility ($\geq+5.00\text{D}$ to $\leq+7.00\text{D}$). Beyond the upper limit of eligibility for randomization ($\geq+7.00\text{D}$), the majority of both optometrists and ophthalmologists would recommend providing a refractive correction, making randomization of infants to observation only questionable ethically (Lyons et al., 2004; Miller et al., 1998). Therefore, these infants will be given treatment (like the treatment group) and observed as a Case Series to better understand the nature of their refractive error development.

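### The allocation rule conflicts at exactly +7.00D: the same infant qualifies both for randomisation and for outright treatment in the case series

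*Combined protocol and SAP*

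**What the plan says.** Two rules route an eligible infant, and each is stated in several places.

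- **Eligibility list.** Infants at ≥+5.00D to ≤+7.00D "will be randomized to treatment or standard therapy (which is observation only"). Infants above +7.00D are treated.
- **Randomization (D.b.i).** The randomised range is again ≥+5.00D to ≤+7.00D. The subsection closes by saying that subjects at +7.00D "or higher will receive treatment as a Case Series".
- **Control group – Standard Therapy (D.b.iii).** No correction is justified for infants at ≥+5.00D to ≤+7.00D. The next sentence starts "Beyond the upper limit of eligibility for randomization", writes that limit as ≥+7.00D, and says most practitioners would correct there, "making randomization of infants to observation only questionable ethically". Later in the subsection, infants from +5.00D up to +7.00D "who are randomized to standard therapy will receive no correction".
- **Case Series Group (D.b.iv).** Infants at ≥+7.00D "will receive treatment (same protocol as infants randomized to the treatment group of this study").

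The Background and Rationale (II) describes "early refractive error between +5.00D to +7.00D, which is what is proposed in this study", without saying whether the endpoint is included.

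**The concern.** An allocation rule should send every eligible infant down exactly one path. Here an infant at +7.00D has two: randomisation, with the possibility of no correction, or spectacles outright. Staff who follow the Randomization subsection meet both instructions in the same place.

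Two things follow. First, the plan's own ethical argument against randomising to observation is attached to ≥+7.00D, so read literally the plan permits randomisation at a value where it calls this questionable. Second, whoever handles such an infant has discretion over whether it enters the randomised comparison. A threshold that decides entry should leave no such discretion.

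**Working it through.** No power or sample-size figure is involved. The check sets the statements side by side and applies them at the boundary.

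| Place | Randomise | Treat outright |
|---|---|---|
| Eligibility list | ≥+5.00D to ≤+7.00D | >+7.00D |
| Randomization (D.b.i) | ≥+5.00D to ≤+7.00D | ≥+7.00D (stated in words) |
| Control group (D.b.iii), rationale | ≥+5.00D to ≤+7.00D | ≥+7.00D |
| Control group (D.b.iii), follow-up | +5.00D up to +7.00D, endpoint unclear | not stated |
| Case Series Group (D.b.iv) | not stated | ≥+7.00D |

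**Tally.** The randomised range is given four times. Three statements explicitly include +7.00D. The fourth does not settle the endpoint: elsewhere, on the correction of a non-emmetropizing eye (D.b.ii), the plan says expressly that the endpoint of an upper limit is included, and it does not do so here. The outright-treatment threshold is also given four times. Three statements include +7.00D and one excludes it.

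**Test values at and either side of the boundary:**

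| Refractive error | Randomise (≤+7.00D) | Treat (>+7.00D, eligibility list) | Treat (≥+7.00D, D.b.i, D.b.iii, D.b.iv) |
|---|---|---|---|
| +6.75D | yes | no | no |
| +7.00D | yes | no | yes |
| +7.25D | no | yes | yes |

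Only +7.00D satisfies two rules. D.b.i conflicts within itself, and so does the rationale in D.b.iii, where the same value is placed inside the range and also beyond its limit. D.b.iv conflicts with the eligibility list and D.b.i.

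**After a correction.** With randomisation at ≤+7.00D and treatment at >+7.00D, or with randomisation at <+7.00D and treatment at ≥+7.00D, each of the three test values falls under exactly one rule.

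**Frequency.** The documents give no distribution of refractive error at enrolment, so the number of infants at exactly +7.00D cannot be calculated.

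**The case against.** The best reply is that this is a drafting slip with an obvious cure. The eligibility list is mutually exclusive, and the Control group text describes the case series as lying past the limit for randomisation, which suggests a strict inequality. The protections for controls also limit the stakes. They are seen on the same schedule as treated infants, and any infant not below +3.50D in each eye at 18 months "will be referred outside the study for an independent evaluation". Under Development of Strabismus (D.f), an infant who develops strabismus leaves study treatment and can receive clinical care outside the study.

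The mitigation stands and keeps the point minor. The appeal to obvious intent stands only in part. Three of the four case-series statements include +7.00D, one of them in words, so a misread symbol cannot explain the conflict. The ethical argument is itself pinned to ≥+7.00D. A reader could infer the opposite intention just as reasonably, and the documents do not decide between them.

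It is also fair to say that a tie-break might sit in the text immediately before the eligibility list, which was not available here. The point therefore rests on the conflicting statements and not on the absence of a tie-break.

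**Conclusion.** The conflict is real, confined to exactly +7.00D, and minor. It rests only on reading the stated bounds literally.

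Three stronger readings go beyond the documents:

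- **That the between-arm comparison is biased.** Routing precedes assignment, so harm would require the person routing the infant to know or guess the next allocation. D.b.i describes a list generated before the study starts, and the available text does not describe concealment. Bias is therefore not shown, but neither can it be ruled out on the ground that routing comes first.
- **That many, or only a few, infants are affected.** The documents support neither statement.
- **That the plan knowingly randomises infants it considers unethical to randomise.** The text is inconsistent at this value; it does not show a decision to do so.

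**What to change.** Use one strict bound everywhere, and have the sponsor state which is intended.

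- **Option A:** randomise ≥+5.00D to ≤+7.00D and treat >+7.00D. This changes the treatment threshold in Randomization (D.b.i), Control group (D.b.iii) and Case Series Group (D.b.iv) to match the eligibility list.
- **Option B**, if the ethical limit is meant to include +7.00D: randomise ≥+5.00D to <+7.00D and treat ≥+7.00D. This changes the randomised range in the eligibility list, D.b.i and D.b.iii, changes the treatment threshold in the eligibility list, and makes the endpoint explicit in the D.b.iii follow-up paragraph.

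The choice is clinical and ethical, so it belongs to the sponsor. Option B needs more edits, but both are a matter of a symbol or phrase in each place. Neither alters the sample size, procedures or analysis. If enrolment is already complete, the sponsor should report which rule was applied and how any infant at exactly +7.00D was routed.
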